6.4. Covariates and Subgroups

Subjects were stratified by (1) pyelonephritis vs. other cUTIs and (2) participating site at randomization. Although the protocol does not define any formal subgroup analyses, for secondary and exploratory efficacy outcomes, analyses of treatment success, clinical cure, and microbiological success at TOC and EOT will be reported by treatment strategy and overall and will additionally be stratified by subgroups including cUTI type, indwelling urinary catheter, obstructive uropathy, recurrent UTI status, diabetes status, age group (<65, ≥65 years), BMI (<30, ≥30 kg/m²), sex, creatinine clearance (≥60 mL/min, <60 mL/min), investigator-adjusted therapy, number of days of antibiotics use (≤7, > 7 days), pathogen at baseline (including further subgrouping by antibiotic susceptibility). Note that subgroup analysis will be performed only for subgroups with total sample size above 10 subjects.

6.5. Missing Data

While all efforts will be made to minimize missing data, some missing data is expected. Whenever possible, subjects terminating from the study early will be given an early termination visit during which all assessments that would have been completed at the EOT visit should be made. The primary analysis will use multiple imputation as detailed in Section 8.4.1. The primary analysis will be repeated using CC populations without imputation. A sensitivity analysis considering various scenarios for the values of the missing data will also be performed.

6.6. Interim Analyses and Data Monitoring

Regular reviews for safety by a DSMB were planned, with the first one occurring approximately 12 months following the enrollment of the first participant. However, this DSMB meeting did not occur since the study was terminated before the 12-month timeline. The DSMB may also review available safety data if a halting rule was met or convene an ad hoc meeting to discuss any issue of safety raised by an investigator, the sponsor, or a member of the DSMB. No halting rules were met in this study. There are no additional formal stopping rules based on safety data assessed in interim safety reviews.

One formal interim analysis of efficacy was scheduled to occur after approximately 40% of subjects completed the trial but will not be performed due to the study closing early.

6.7. Multicenter Studies

This is a multicenter study with a total of 6 sites participating in the trial which were: University of Rochester, Emory University Hospital-Midtown, Grady Memorial Hospital, Hope Clinic of the Emory Vaccine Center, Northwestern University, and University of Iowa. Only 5 of the 6 sites had enrolled subjects by the time of study closure; Northwestern University did not enroll any subjects. During randomization, subjects are stratified by participating site, but in the primary analysis, data will be pooled across all clinical sites.

6.8. Multiple Comparisons/Multiplicity

The results presented in this report will not be adjusted for multiple comparisons. The 5% significance level will be used for all tests.

7. STUDY SUBJECTS

7.1. Disposition of Subjects

Reasons for screening failures will be summarized in [Table 10](#). The completion status and reasons for early termination or treatment discontinuation will be summarized in [Table 6](#). A listing of subjects who discontinued treatment or terminated from study follow-up and the reason will be included in [Listing 1](#). A subject could be discontinued early due to an AE (serious or non-serious), being diagnosed with bacteremia with a uropathogen, loss to follow-up, non-compliance with study, voluntary withdrawal by subjects/subject's LAR, withdrawal at the investigator request, termination of the site by the sponsor, termination of the study by the sponsor, death, lack of eligibility at enrollment, or becoming ineligible after enrollment.

The composition of analysis populations, including reasons for subject exclusion, by treatment arm, will be presented in [Table 7](#). [Table 8](#) will present the number of enrolled subjects who received study product by site and treatment group.

A flowchart showing the disposition of study subjects, adapted from the CONSORT Statement will be included in [Figure 1](#). This figure will present the number of subjects screened, enrolled and randomized, received study drug, included in the micro-ITT population, and received an investigator-adjusted therapy by treatment arm.

7.2. Protocol Deviations

A summary of subject-specific protocol deviations will be presented by the reason for the deviation, the deviation category, and treatment group for all subjects in [Table 2](#). All subject-specific protocol deviations and non-subject specific protocol deviations will be presented in [Listing 2](#) and [Listing 3](#), respectively. Major protocol deviations will be discussed.

8. EFFICACY EVALUATION

Tables containing an asterisk (*) in the title indicate tables and figures that will be provided to the PI for publication in the primary manuscript while the rest of the tables, figures, and listing will be provided to the FDA in the abbreviated CSR.

8.1. Primary Efficacy Analysis

8.1.1. Analysis of Treatment Success at TOC in the Micro-ITT Population

The primary efficacy endpoint is the difference in the proportion of subjects achieving treatment success at TOC between Strategy 1 and Strategy 2. The primary efficacy analyses will be performed for the micro-ITT population.

The null hypothesis corresponding to the primary analysis of this study was:

H_0 : The treatment success at TOC is not conditional on the treatment strategy.

This test will be conducted using the Wald test from linear regression using the multiple imputation model.

The primary analysis will use multiple imputation with a linear regression model without rounding to impute missing values for treatment success at TOC in the micro-ITT population [1 and 2].

Although the linear regression without rounding can sometimes yield implausible imputed values of treatment success, Horton et.al (2003) [2] showed this method yields an unbiased estimate of the binomial proportion.

- Let Y_1, Y_2, \dots, Y_N be independent and identically distributed (iid) Bernoulli random variables
- Let $p = E(Y_i)$ be the probability of success
- Assume that only n out of the N Bernoulli data points are observed; the rest are missing. For simplicity, assume Let Y_1, Y_2, \dots, Y_n are observed and Let Y_{n+1}, \dots, Y_N are missing. We further assume that data is Missing Completely at Random (MCAR).

For estimating p , the minimum variance unbiased estimate (MVUE) of p denoted by \hat{p} which is simply the mean of observed data, i.e.,

$$\hat{p} = \frac{1}{n} \sum_{i=1}^n Y_i$$

Rubin and Schenker (1986) [4] proposed using a full normal imputation method to impute missing values Y_{n+1}, \dots, Y_N which assumes that the Y_i are iid from normal distribution with mean p and variance σ^2 . This method follows the following algorithm to generate the missing values.

This full normal imputation method without rounding incorrectly assumes a normal distribution and can sometimes yield implausible imputed values (above 1 or below 0). However, it produces an unbiased estimate of the probability of success p .

Allison (2005) [1] showed that this approach can be extended to allow covariates in the model. Hence, Using simulation studies, Allison showed that multiple imputation using linear regression performed well in estimating regression coefficients in different missing data scenarios (MCAR, MAR) even when compared to logistic regression. The added benefit of using the linear regression model is that it directly provides proportion differences along with their 95% CI after applying PROC MIANALYZE to the model fits from the M multiply imputed datasets.

Due to the low sample size at the close of the study, the results of this hypothesis test should be interpreted with care since the required power to conclude a significant difference was not achieved. An estimate of the composite cure and composite cure difference between the two strategies along with its 95% Wald CI (no continuity correction) and p-value will be provided.

Details of multiple imputation methods for efficacy outcomes specific to DMID-15045 are described in Section 8.4.1.

Step 1: A multiple regression model: $Y_i = \beta_0 + \beta_1 X_1 + \beta_2 X_2 + \beta_3 X_3 + \dots + \beta_c X_c + \epsilon_i$, $\epsilon_i \sim N(0, \sigma^2)$ where Y_i represents the indicator for composite cure and X_c are the covariates described in Section 8.4.1 to be used in the multiple imputation model to generate M multiply imputed datasets.

Step 2: A simple linear regression model $Y_i = \beta_0 + \beta_1 trt + \epsilon_i$ will be fit on each of the m multiply imputed datasets. Estimates of composite cure from each of the m models will be given by the β_1 which represent the difference in treatment success between the two strategies.

Step 3: The final composite cure will be obtained by combining M estimates of composite cure estimates using PROC MIANALYZE as described in Section 8.4.1. The p-value for trt from this step will be used for hypothesis testing. The null hypothesis will be rejected if the p-value is less than or equal to 0.05 and will conclude that the treatment success at TOC is conditional on treatment strategy. If the composite cure estimate for strategy 1 is above that of strategy 2 and the p-value is ≤ 0.05 , then we can conclude that strategy 1 is superior to strategy 2 at TOC. Similarly, if the composite cure estimate for strategy 2 is above that of strategy 1 and the p-value is ≤ 0.05 , then we can conclude that strategy 2 is superior to strategy 2 at TOC. If the null hypothesis is not rejected, we will conclude that evidence from the trial is insufficient to conclude that either strategy is superior.

The proportion of subjects with composite cure at TOC in each strategy will be provided. The difference in the proportion of subjects having composite cure at TOC between Strategy 1 and Strategy 2 along with the 95% Wald CI (no continuity correction) for the treatment difference from Step 3 above will be provided (Table 20). A listing of urine culture results used for calculating microbiological cure is provided in Listing 8. A listing of UTI signs and symptoms used for calculating clinical cure at TOC is provided in Listing 9.

8.2. Secondary Efficacy Analyses

8.2.1. Analysis of Composite Cure at EOT in the Micro-ITT Population, Performed in an Analogous Manner to the Primary Analysis

The secondary efficacy endpoint is the difference in the proportion of subjects achieving treatment success at EOT between Strategy 1 and Strategy 2. The secondary efficacy analyses will also be performed for the micro-ITT population.

The null hypothesis corresponding to the secondary analysis of this study was:

H_0 : The probability of success at EOT is not conditional on the treatment strategy.

The secondary analysis will be conducted in a similar manner as the primary analysis by using multiple imputation with a linear regression model to impute missing values for treatment success at EOT in the micro-ITT population. Details of the multiple imputation methods are described in Section 8.1.1. and Section 8.4.1.

The proportion of subjects with composite cure at EOT in each strategy will be provided. The difference in the proportion of subjects having composite cure at EOT between Strategy 1 and Strategy 2 along with the 95% CI for the treatment success difference will be provided (Table 20). A listing of individual

microbiological response data at EOT is provided in [Listing 8](#) and a listing of UTI symptoms used for calculating clinical cure at EOT is provided in [Listing 9](#).

8.2.2. Sensitivity Analyses of Composite Cure at TOC and EOT in the Micro-ITT Population

A sensitivity analysis will be performed for the primary analysis using subjects in the micro-ITT population that have no missing treatment success values at TOC (CC-TOC Population) and EOT (CC-EOT Population). These subjects will be analyzed as randomized without imputation. The treatment success will be estimated from this model: $Y_i = \beta_0 + \beta_1 trt + \epsilon_i$

For this analysis, estimate of treatment success in each strategy, the difference in the proportion of subjects in this population having composite cure at TOC and EOT between Strategy 1 and Strategy 2 with the 95% Wald CI (no continuity correction), and p-value will be provided in [Table 21](#). Additionally, a sensitivity analysis of best/worst case scenarios using various percentages of missing composite cure is provided in [Table 24](#) for TOC and [Table 25](#) for EOT.

8.3. Exploratory Efficacy Analyses

Multiple exploratory efficacy analyses will be performed for this study using subjects in the micro-ITT population with no missing values at EOT and TOC, the endpoints of interest (CC-EOT and CC-TOC Populations, respectively).

A comparison of the proportion of subjects achieving clinical cure and microbiological success at EOT and TOC between Strategy 1 and Strategy 2 will be provided in [Table 20](#) using micro-ITT population and [Table 21](#) using CC populations. Analysis of clinical cure will be repeated using ITT analysis population with multiple imputation ([Table 22](#)) and using all subjects with non-missing clinical cure without multiple imputation ([Table 23](#)).

Comparison of subjects achieving treatment success, clinical cure, and microbiological cure at TOC between the two treatment strategies, including the 95% CI, stratified by multiple subgroups including cUTI type, indwelling urinary catheter, obstructive uropathy, recurrent UTIs, baseline characteristics (Age, BMI, sex, creatinine clearance etc.), adjustment of therapy per protocol, number of days of unique antibiotics prescribed between randomization and TOC (≤ 7 days vs. > 7 days), and susceptibility to various pathogens at baseline will be provided in [Table 26](#), [Table 28](#), [Table 29](#), and [Table 32](#), respectively. Similar comparisons for the proportions of subjects achieving treatment success, clinical cure, and microbiological cure at EOT between Strategy 1 and Strategy 2 will be provided in [Table 27](#), [Table 30](#), [Table 31](#), and [Table 33](#), respectively. Note that [Table 5](#) provides a list of antimicrobial categories for several antibiotics will be used to determine whether a pathogen is multidrug resistant [5].

8.4. Imputation of Missing Data

8.4.1. Multiple Imputation of Missing Values of Treatment Success at TOC and EOT

Primary and secondary analyses depend on multiple imputation of treatment success at TOC and EOT, respectively. First, a table showing the number and percentage of missing data for each outcome at EOT and TOC will be presented in [Table 18](#). In order to use the MI model to adjust for bias caused by missing data, we assume that data is missing at random (MAR). To test this assumption, we will fit a logistic model for missing data indicator D (1 if missing, 0 if non-missing) adjusting for covariates of the MI model listed below. Parameter estimates, 95% confidence intervals, and p-values from this model will be provided in

Table 19 at TOC and at EOT. If some of these covariates have a significant relationship with the missing data indicator ($p\text{-value} \leq 0.05$), then the MAR assumption is more likely than MCAR.

In case of missing treatment success at TOC or EOT, multiple imputations of missing treatment success at TOC or EOT will be performed independently, and each subject will have their missing endpoints imputed independently of other subjects' imputations using a subject-specific imputation model. The pseudocode shown below details how missing data for treatment success at TOC (or EOT) will be imputed using m multiply imputed datasets from linear models. The following covariates will be considered for the MI model: treatment strategy, site indicators, age, sex, pyelonephritis status, and number of bacterial species. The number of imputed, m , datasets will be chosen based on the average percent of missing data. Default value will be $m=20$ since sample size calculation assumed a 20% drop-out rate. Similar models will be fit for clinical cure and microbiological success.

As a first step to multiple imputation, an ordered list of variables to include in the subject-specific imputation model will be constructed. Ordering is specified so that exact imputation results from final data are prespecified may be replicated in SAS (using seeds described below). The complete ordered list of variables for the imputation models for treatment success, clinical cure, and microbiological success at TOC and EOT is below:

- Treatment Strategy (Strategy 2 is the reference)
- Indicator of subject enrolled at the site with the second most number of subjects enrolled (binary indicator)
- Indicator of subject enrolled at the site with the third most number of subjects enrolled (binary indicator)
- Indicator of subject enrolled at the site with the fourth most number of subjects enrolled (binary indicator)
- Indicator of subject enrolled at the site with the least number of subjects enrolled (binary indicator)
 - Note: the site with the most number of subjects enrolled is reference for site. Language is written to allow for an arbitrary number of sites. In the event of a number of ties for the number of subjects enrolled, tied sites will be ordered in ascending alphanumeric order in the list of model variables.
- Age at enrollment
- Sex (Male is the reference)
- Indicator for pyelonephritis (No is the reference)
- Number of species detected in the urine at baseline (1 is the reference)

The actual list of MI model variables for each subject-specific imputation model will follow the ordering above but omit variables with missing values. The below pseudo-code / SAS code outlines the creation of 20 multiple imputation datasets. Note that the seeds used in the actual analysis must follow the specification given in the pseudo-code and subjects must be processed in the order described in the pseudo-code. Clinical cure and microbiological success will simultaneously be imputed with composite cure at each respective time point. The pseudo-code is in terms of TOC endpoints, but the general logic is also applicable to the EOT.

*Outcome variables: trtsuccess clincure microsuccess

DEFINE i=index variable for subjects having treatment success imputed.

Subjects requiring imputation are sorted in ascending order
by PATID.

DEFINE N=number of subjects requiring imputation

DEFINE g&i=analysis dataset containing predictors and treatment success for
CC-TOC subjects as well as subject i (only one subject not in
CC-TOC included). Note that CC-TOC subjects that are missing a value
for one or more variables in the subject-specific imputation model are excluded.

DEFINE imp_g&i = g&i, with 20 imputed values for the missing treatment success
added by PROC MI

DEFINE &&modelVars_&i = list of observed variables in subject i (site1, site2, site3, site4, age, sex,
treatment strategy, pyelonephritis, Nbacterias), to be used for imputation of treatment success, clinical cure,
and microbiological cure.

Step 1: Imputation model: This model will generate 20 datasets with each dataset containing original complete data along with imputed values for subjects with missing endpoint.

```
%do i=1 %to &N;
```

```
PROC MI data= g&i out= imp_g&i seed= 22131&i NIMPUTE=20 noprint;
  Var &&modelVars_&i trtsuccess_TOC clincure_TOC microsuccess_TOC;
  monotone regression(trtsuccess_TOC = &&modelVars_&i);
  monotone regression(clincure_TOC = &&modelVars_&i);
  monotone regression(microsuccess_TOC = &&modelVars_&i);
```

```
run;
```

```
%end;
```

imp_g&i will be subset to contain only rows for the subjects with imputed treatment success, clinical cure,
and microbiological success and merged together and with CC-TOC data to create the twenty complete
multiply imputed datasets

Step 2: Analysis model: This model will fit regression models to the 20 complete datasets to obtain parameter estimates for treatment success, clinical cure, microbiological success.

```
proc reg data= imp_g outest= out_trts covout noprint;
```

```
model trtsuccess= trt /clb alpha=0.05;
```

```
by _imputation_;
```

```
run;
```

```
proc reg data= impdata outest= out_clinc covout noprint;
model clincure= trt /clb alpha=0.05;
by _imputation_;
run;

proc reg data= impdata outest= out_micros covout noprint;
model microsucceed= trt/clb alpha=0.05;
by _imputation_;
run;
```

Step 3: Combine estimates from models in step 2 to obtain overall estimates summarized over 20 imputed datasets;

```
proc mianalyze data= out_trts alpha = 0.05;
modeleffects trt;
ods output ParameterEstimates=parms_trts;
run;

proc mianalyze data= out_clinc alpha = 0.05;
modeleffects trt;
ods output ParameterEstimates=parms_clinc;
run;

proc mianalyze data= out_micros alpha = 0.05;
modeleffects trt;
ods output ParameterEstimates=parms_micros;
run;
```

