2. INTRODUCTION

This is a Phase IV, multi-center, open-label randomized pragmatic superiority clinical trial with a primary objective to evaluate the efficacy of Strategy 1 (initial OR step-down with fosfomycin 3 grams, oral, once daily) vs. Strategy 2 (initial OR step-down with levofloxacin 750 mg, oral tablet once daily) in terms of treatment success rates for patients with complicated urinary tract infections (cUTIs). Each strategy allowed for a subsequent investigator-directed adjustment to another adequate oral therapy if needed. Subjects were randomized 1:1 to receive oral therapy from Strategy 1 vs. Strategy 2. Subjects were stratified by (1) pyelonephritis vs. other cUTIs and (2) participating site.

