5. SAMPLE SIZE CONSIDERATIONS

This is a Phase IV multicenter, open-label, randomized pragmatic superiority clinical trial comparing two strategies for step-down oral therapy for cUTI. The basic null hypothesis of this trial is:

H0: The probability of success (clinical cure and microbiological cure) at TOC is not conditional on the treatment strategy.

This hypothesis testing question will result in one of three statements regarding the results of this trial:

1. Strategy 1 is superior to Strategy 2.
2. Strategy 2 is superior to Strategy 1.
3. Evidence from the trial is insufficient to conclude that either strategy is superior.

The primary analysis will use the micro-ITT population, defined as all randomized subjects who have a positive baseline bacterial culture of urine. Subjects will not be excluded from this population based upon events that occurred post-randomization (e.g., loss to follow-up). An assumption of 92% micro-ITT eligibility is made for the sample size calculations. If 634 subjects are enrolled with 1:1 allocation, 291 subjects per arm would be expected to qualify for the micro-ITT population. Assuming a 10% difference in treatment success at TOC, with 80% success for one strategy and 70% success for the other strategy, there will be 80% power to reject the null hypothesis using a two sided ztest (without continuity correction), with a Type I error rate of 5%. These calculations assume an interim analysis after 40% of subjects have completed the study, with Type I error controlled using Lan DeMets with an O'Brien Fleming spending function. The specific success rates of 70% and 80% are based on a 10% clinically significant difference an approximate rate of success consistent with example calculations in the FDA guidance for cUTI studies. Sample size calculations were computed using PASS 2008 software. The calculations do not adjust for dropout, because analysis methods will include subjects that have dropped out early, assuming they meet micro-ITT criteria (Section 6.3.1).

If true success rates are instead 65% and 75%, there will be 75% power to conclude a difference in the strategies. If true success rates are 80% and 90%, there will be 92% power to conclude a difference.

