However, this study was terminated early due to slow enrollment with only 62 subjects enrolled in the study. Only 48 out of the 62 subjects were eligible to be in the micro-ITT analysis population. Using the same assumptions of 10% difference in the treatment success, there was only a 12% power to reject the null hypothesis using a two sided z-test (without a continuity correction) with a Type I error rate of 5. Given this low power, the efficacy results should be interpreted with caution as to not make any conclusions regarding the superiority of either strategy.

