14.2 Efficacy/Microbiology Data

Table 18: Number and Percentage of Missing Data by Study Endpoint, Timepoint, and Treatment Group*

| Endpoint | Strategy 1 (N=X) | | Strategy 2 (N=X) | | All Subjects (N=X) | |
|-----------------------|---------------------|---|---------------------|---|-----------------------|---|
| | n | % | n | % | n | % |
| End of Therapy | | | | | | |
| Composite Cure | x | x | x | x | x | x |
| Clinical Cure | | | | | | |
| Microbiological Cure | | | | | | |
| Test of Cure | | | | | | |
| Composite Cure | | | | | | |
| Clinical Cure | | | | | | |
| Microbiological Cure | | | | | | |

N = Number of subjects in the micro-ITT population in the respective treatment group.

Clinical cure is defined as: 1) Resolution of UTI symptoms from presentation and 2) No new UTI symptoms and 3) Avoidance of parenteral antibiotic therapy, in or out of hospital, at any time after randomization OR oral antibiotic therapy different from per protocol.

Microbiological cure is defined as a reduction of the pathogen found at presentation to <104 CFU/mL for non-catheter specimens or < 103 for catheter specimens on urine culture.

Treatment success (composite cure) is defined as a combination of clinical cure and microbiological success.

Table 19: Verification of the MAR Missing Data Assumption Using Logistic Regression Model with Missing Composite Cure Indicator as the Outcome - Micro-ITT Population*

| Model Parameter | Parameter Category | Parameter Estimates | 95 % CI | P-value |
|--|--------------------|---------------------|----------|---------|
| End of Therapy | | | | |
| Intercept | N/A | x.x | x.x, x.x | x.xxx |
| Treatment | Strategy 2 | - | - | - |
| | Strategy 1 | x.x | x.x, x.x | x.xxx |
| Site 1 | No | - | - | - |
| | Yes | x.x | x.x, x.x | x.xxx |
| Site 2 | No | - | - | - |
| | Yes | x.x | x.x, x.x | x.xxx |
| Site 3 | No | - | - | - |
| | Yes | x.x | x.x, x.x | x.xxx |
| Site 3 | No | - | - | - |
| | Yes | x.x | x.x, x.x | x.xxx |
| Age | N/A | x.x | x.x, x.x | x.xxx |
| Sex | Male | - | - | - |
| | Female | x.x | x.x, x.x | x.xxx |
| Pyelonephritis | No | - | - | - |
| | Yes | x.x | x.x, x.x | x.xxx |
| Number of bacterial species in the urine | 1 | - | - | - |
| | 2 | x.x | x.x, x.x | x.xxx |
| | 3 | x.x | x.x, x.x | x.xxx |
| Test of Cure | | | | |
| Intercept | N/A | x.x | x.x, x.x | x.xxx |
| Treatment | Strategy 2 | - | - | - |
| | Strategy 1 | x.x | x.x, x.x | x.xxx |
| Site 1 | No | - | - | - |
| | Yes | x.x | x.x, x.x | x.xxx |

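### SAP 8.4.1 and Table 19 present a logistic model of missingness as a test of MAR; it can only count against MCAR, and it is too large for 48 subjects

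*SAP*

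**What the plan says.** SAP 8.4.1 assumes MAR so that multiple imputation can adjust for bias from missing outcomes. It continues: "To test this assumption, we will fit a logistic model for missing data indicator D", with the imputation covariates as predictors: treatment strategy, site indicators, age, sex, pyelonephritis and number of bacterial species. The decision rule is that if some covariates reach p ≤ 0.05, "then the MAR assumption is more likely than MCAR". MNAR does not enter the rule, and no reading is given for a non-significant result.

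The output is Table 19, "Verification of the MAR Missing Data Assumption Using Logistic Regression Model with Missing Composite Cure Indicator as the Outcome", with estimates, 95% confidence intervals and p-values at EOT and TOC. It carries the asterisk that SAP sections 1 and 8 reserve for the primary manuscript. No fallback is given for a model that fails to converge or separates.

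On size, SAP section 5 states: "Only 48 out of the 62 subjects were eligible to be in the micro-ITT analysis population". Elsewhere, SAP 8.2.2 plans Tables 24 and 25, which vary the proportion of missing outcomes counted as success from 0% to 100% in each arm. Section 9.1 plans Table 16, a description of baseline characteristics by arm and missing-outcome status.

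**The concern.** Whether missingness depends on the unseen outcome is what separates MNAR from MAR. A model containing only the missing-data indicator and baseline covariates has no term for that outcome. A covariate that predicts missingness counts against MCAR but fits MAR and MNAR equally well, and a covariate that does not predict it supports neither. Calling this a test, and publishing it as verification, tells readers that the assumption behind the primary imputation was checked when it cannot be.

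The second problem is practical. With about one missing outcome per fitted slope, some site or species category is likely to contain only observed or only missing outcomes. The maximum-likelihood coefficient for that category then diverges, and its Wald interval and p-value mean nothing. A published table could contain several such rows, and the 0.05 rule would be applied to them.

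**Working it through.** **1. The SAP's own figure, to fix n.** SAP section 5 says "there was only a 12% power to reject the null hypothesis using a two sided z-test (without a continuity correction". The level is printed there as 5 and is read here as 5%. The other inputs are 48 subjects and success rates of 80% and 70%. The split of the 48 is not given; "Subjects were randomized 1:1 to receive oral therapy from Strategy 1 vs. Strategy 2" suggests 24 per arm. With pooled variance under the null:

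z = (0.10 × √24 − 1.96 × √(2 × 0.75 × 0.25)) / √(0.8 × 0.2 + 0.7 × 0.3) = (0.490 − 1.200) / 0.608 = −1.17

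Power = Φ(−1.17) = 12.1%. The stated 12% reproduces, so n = 48 with about 24 per arm is a sound basis.

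**2. What the model can see.** Let D be the missing indicator, Y the outcome and X the covariates. The model estimates P(D=1 | X) = Σ P(D=1 | X, y) P(y | X). If D depends on Y only and Y is unrelated to X, the sum is the same for every X. The joint distribution of D and X is then identical to that under MCAR, so any test built on D and X behaves identically.

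Illustration (assumed rates): true success 75%, P(missing | success) = 12.5%, P(missing | failure) = 42.5%.

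- Missing: 0.75 × 0.125 + 0.25 × 0.425 = 20%.
- Observed success: 0.75 × 0.875 / 0.80 = 82.0%.

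A success rate is off by 7 points and Table 19 would show nothing unusual.

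**3. Size of the model.** Five enrolling sites (SAP 6.7) give 4 indicators. Treatment, age, sex and pyelonephritis add 4. Species adds 2 with the 1/2/3 coding in Table 19, or 1 as a single term. That makes 10 or 9 slopes. At 20% missing, 0.20 × 48 = 9.6 events, or 0.96 to 1.07 events per slope.

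**4. Separation.** Datasets of 48 (24 per arm, 5 sites) were simulated with missingness unrelated to any covariate, and separation was detected by linear programming. Assumed, because the documents do not give them: site splits from even to 50/25/13/8/4%; one, two or three species from 85/12/3% to 50/30/20%; several mixes of sex and pyelonephritis. There were 300 to 1,000 runs per setting, so the Monte Carlo standard error is at most √(0.25/300) = 2.9 points.

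| Missing | 10 slopes (Table 19 coding) | 9 slopes (single species term) |
|---|---|---|
| 10% (5 of 48) | 99–100% | 96–100% |
| 20% (10) | 58–95% | 51–89% |
| 30% (14) | 27–92% | 16–79% |
| 40% (19) | 9–80% | 7–66% |
| 50% (24) | 3–82% | 4–61% |

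A repeat gave 52 to 98% at 20% missing and 11 to 88% at 40%. Taken together, the ranges are about 50 to 98% and 7 to 88%. At 20% missing the separation is almost always quasi-complete (complete in at most 0.3% of runs): the model returns output, but the affected rows are unusable.

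**The case against.** The strongest reply is that the SAP's only stated inference is modest. It assumes MAR, and the rule compares MAR with MCAR, a contrast on which such a model does bear. That is right about the rule. It does not rescue the sentence that calls the model a test of MAR, or the title of Table 19.

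Second, nothing depends on the table. No step in SAP 8.1.1 or 8.4.1 changes the imputation model, population, estimate or test according to its p-values. Departures from MAR are addressed in Tables 24 and 25, which have assigned manuscript positions, and section 5 already warns against any superiority conclusion. This stands. A reader might infer that the primary result is invalidated or altered by Table 19; the documents do not support that.

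Third, the separation rate rests on figures the documents do not give. This also stands. A reader might infer that the model would usually be separated at this size. That holds at 20% missing or less in every setting tried, but not in general at 30% or more. The 20% itself is a planning figure: SAP 8.4.1 and Protocol 11.3.2 call it an assumed drop-out rate, while SAP section 5 says the sample size does not adjust for dropout.

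Finally, a reader might want a figure for bias in the treatment difference. The documents describe no missingness mechanism, so none can be given.

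**Conclusion.** Wrong as written, with limited consequence. The description of the logistic model as a test of MAR, and of Table 19 as its verification, is incorrect whatever the data show; this needs no assumption about the missing fraction. The overfitting is conditional: about 50 to 98% of datasets separated if roughly 20% of outcomes are missing, and about 7 to 88% at 40%, across assumed site and species mixes. The 7-point shift in the illustration concerns a single success rate under an assumed mechanism and is not an estimate for this trial. The primary estimate is unaffected, and the tables that do address departures from MAR are already planned.

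**What to change.** - Retitle Table 19 *Baseline predictors of missing outcome*.
- In SAP 8.4.1, delete the clause saying the model tests the assumption, and delete the p ≤ 0.05 rule.
- State that MAR cannot be tested from the observed data, and that Tables 24 and 25 are the assessment of departures from it.
- Fit the Table 19 model with Firth penalisation, keeping the imputation covariates and pooling small sites if needed. Alternatively, drop the model and rely on the descriptive Table 16.

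The cost is a few sentences, a table title and one option or simplification in a supporting model. The imputation, the primary analysis and the data collected do not change.
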